# 5.3 Procedures for handling patients incorrectly enrolled, randomised or administered investigational product

Patients who fail to meet the inclusion/exclusion criteria should not, under any circumstances, be enrolled or randomised to receive IP. There can be no exceptions to this rule.

#### 31(65)

Where patients that do not meet the selection criteria are enrolled in error or incorrectly started on treatment, or where patients subsequently fail to meet the study criteria post initiation, the investigator should inform the AstraZeneca study physician or delegate immediately.

Patients who are incorrectly enrolled but are not yet randomised or initiated on treatment should be withdrawn from the study. In the event that a patient has been randomised and administration of study medication has started in error despite best efforts to ensure that the inclusion and exclusion criteria were adhered to by the investigator, with respect to continuing administration of study medication, medical judgment should apply on a case-by-case basis.

The likely benefits and risks to the patient should be assessed and a discussion should occur between the study physician and the investigator regarding whether to continue or discontinue the patient from treatment.

In cases where it could not be excluded that exposure to IP might compromise individual safety of the specific patient, the administration of IP must be stopped. Otherwise, the patient may continue on study treatment. In situations where an agreement cannot be reached, the patient should have the IP stopped. If decided to stop the intake of IP, the procedures described in Section 5.8.1 must be followed.

The AstraZeneca physician is to ensure all such contacts are appropriately documented.

# 5.4 Blinding and procedures for unblinding the study

# 5.4.1 Methods for ensuring blinding

The Sponsor, Investigators, study staff participating in patient care or clinical evaluations, and patients will be blinded to IP assignment.

The treatment allocation will be kept strictly within ublinded nurses to safeguard the integrity of the blinding of Investigators and patients, and hence to minimize any possible bias in data handling.

# 5.4.1.1 Unblinded nurse and unblinded monitor

The approach of using an unblinded nurse at hospital is a way to ensure blinding throughout the study. The unblinded nurse will be responsible for preparing the blinded IP. The open labelled esomeprazole powder and cimetidine solution for the double blinded infusion treatment phase will be packed in separated boxes. Only the unblinded nurse can open the boxes. The open labelled esomeprazole powder and cimetidine solution will be properly prepared by the unblinded nurse and put into a blinded labelled infusion bag before use by the blinded nurse, according to the separate instructions. The unblinded nurse must not participate in the care of patients. In addition to the blinded monitor, AstraZeneca will assign an unblinded monitor (see Section 9.3) to confirm drug accountability. The unblinded monitor must not be involved in other parts of the study conduct.

### 5.4.1.2 The site patient randomisation list / code envelope

The site patient randomisation list is a document with a set of the randomisation codes which are pre-allocated to the hospital.

The individual code envelope will indicate the treatment arm for each randomised patient.

The site patient randomisation list / the individual code envelope will be provided to the unblinded nurse only for the preparation of the blinded labelled infusion bag. The unblinded monitor will access the site patient randomisation list / the individual code envelope during the site drug accountability monitoring activities. The information in the site patient randomisation list / the individual code envelope must be kept strictly from other personnel involved in the conduct of the study, and at a secure location until the end of study.

## 5.4.2 Methods for unblinding the study

The eligible patient will be randomised with a unique individual randomisation code. The individual randomisation code must not be broken by the investigator(s) or study staff except in medical emergencies when the appropriate management of the patient requires knowledge of the treatment randomisation. If any blinded information is broken, the date, the time and the reason must be documented / recorded via IVRS/IWRS and in any associated AE report. The investigator is responsible for ensuring this documentation is maintained and reports the action to AstraZeneca, without revealing the treatment given to the patient and the blinded AstraZeneca staff.

AstraZeneca retains the right to break the randomisation code for SAEs that are unexpected and are suspected to be causally related to an IP and that potentially require expedited reporting to regulatory authorities.

Randomisation codes will not be broken for the planned analyses of data until all decisions on the evaluability of the data from each individual patient have been made and documented.

Except for safety reasons, patients, investigators, all blinded site staff and blinded monitors will have no access to the individual treatment allocation until after the finalization of the Clinical Study Report (CSR).

# 5.5 Treatments

# 5.5.1 Identity of investigational product(s)

The IPs to be used in the study are described in Table 2. Each vial of esomeprazole and each ampoule of cimetidine will be labelled and packed into labelled boxes. Commercial available Esomeprazole tablets will be used and labelled with study specific labels.

Product Name	Dosage form and strength	Manufacturer
Esomeprazole (Nexium®)	Powder for solution for infusion, 40 mg (as esomeprazole sodium 42.5 mg)	AstraZeneca
Cimetidine (Tagamet®)	Solution for infusion, 200mg	
Esomeprazole (Nexium®)	Tablet, 40 mg (as esomeprazole magnesium trihydrate 22.3 mg)	AstraZeneca

## Table 2Investigational Product

#### 5.5.2 Doses and treatment regimens

For eligible patients randomisation followed by i.v. treatment with IP, either esomeprazole or cimetidine should start as soon as possible after the initial primary haemostasis. Start of i.v. treatment must occur within 24 hours after first presentation to the hospital. If the patient is already hospitalised, i.v. treatment should be started within 24 hours after first sign or symptom of upper gastrointestinal bleeding. The 72 hours randomised i.v treatment is followed by a 27 days oral treatment with esomeprazole tablets 40 mg.

If the patient reaches the events of significant rebleeding, endoscopic re-treatment and/or surgery due to rebleeding during the i.v treatment phase, study treatment will be stopped and the patient will be treated according to local guidelines. The patient should continue the study and when the clinical situation permits oral treatment with esomeprazole tablets 40 mg should be initiated and continue to the follow up visit. If i.v. treatment is stopped due to other reason, eg technical failure, double-blind treatment should be re-initiated as soon as the clinical situation permits.

If the patient reaches the events of significant rebleeding, endoscopic re-treatment and/or surgery due to rebleeding during the open label esomeprazole 40 mg q.d. treatment phase, study treatment will be temporarily stopped and the patient will be treated according to local guidelines. The patient should continue the study and when the clinical situation permits oral treatment with esomeprazole tablets 40 mg should be restarted and continue to the follow up visit.

#### 5.5.2.1 Randomised i.v. treatment

During the 72 hours i.v. treatment each randomised patient will receive one of the following treatment regimens:

#### **Esomeprazole treatment:**

Esomeprazole i.v.	Given as 80 mg bolus infusion during 30 min	
Esomeprazole i.v.	8 mg/h constant infusion during 71.5 hours	

34(65)

#### **Cimetidine treatment:**

Cimetidine i.v.

Given as 200 mg bolus infusion during 30 min

Cimetidine i.v.

PLEASE CHECK ITS VALIDITY BEFORE USE

AN ELECTRONIC DOCUMENT.

ЪО

PRINTED COPY

TS A

THIS

60 mg/h constant infusion during 71.5 hours

Both the esomeprazole powder for solution for infusion and cimetidine solution for infusion will be reconstituted with 0.9% sodium chloride solution for infusion (supplied by clinical sites ) and put into 100 ml infusion bag before use, to ensure a final volume of 100 ml. Detailed handling instructions regarding preparation of infusion solution will be provided by AstraZeneca.

For the 30 minutes i.v. treatment, the entire volume of one bag (corresponding to 80 mg esomeprazole or 200 mg cimetidine) will be administered i.v. at a rate of 200 ml/h. The constant rate infusion will be administered i.v. at a rate of 10 ml/h over 71.5 hours. During the constant rate infusion, the infusion bag (corresponding to 80 mg esomeprazole or 600 mg cimetidine) should be changed every 9 ( $\pm$  1) hours. The prepared solution can be kept at below 30 degrees in normal in-door light up to 12 hours. In order to ensure blinding, the prepared solution not used within 12 hours from preparation must be returned to the unblinded nurse.

## 5.5.2.2 Oral treatment with esomeprazole 40 mg

After the i.v. treatment, all patients will be treated orally with esomeprazole 40 mg tablet once daily for 27 days.

If the infusion is terminated before 8.00 a.m. the first oral dose is given the same day. If the infusion is terminated after 8.00 a.m. the first oral dose is given the next day in the morning.

The esomeprazole tablets should be taken before breakfast with a glass of water. The tablets must not be chewed, crushed or divided, but should be swallowed whole.

### 5.5.3 Dose Adjustment

In the patients with eGFR 30-50 ml/min x  $1.73m^2$ , the cimetidine constant infusion dose should be reduced to 30 mg/h, which means only half the amount of cimetidine (300 mg) should be added to the infusion bag in order to keep the infusion rate the same (10 ml/ h). The i.v. bolus dose of cimetidine (200 mg) should not be changed. It is the investigator's responsibility to make sure that the unblinded nurse receives the information about the need for dose adjustment of cimetidine before the IP preparation.

# 5.5.4 Labelling

Labels will be prepared in accordance with Good Manufacturing Practice (GMP) and local regulatory guidelines. The labels will fulfil GMP Annex 13 requirements for labelling. Label text will be translated into local language.

Packing and labelling will be carried out at

### 35(65)

Each vial and ampoule will be labelled with an unblinded tear-off label. The tear-off part is to be inserted into the source data documentation, which is only accessable for the unblinded nurse and unblinded monitor. The IP boxes with esomeprazole vials and cimetidine ampoules and the commercial boxes with esomeprazole tablets will be labelled with an unblinded single panel label. For the infusion bags, blinded tear-off labels will be provided together with the IP boxes of esomeprazole vials and cimetidine ampoules. The infusion bag will be supplied by the clinical sites and the unblinded nurse will put the blinded tear-off label on the infusion bag after the preparation.

# 5.5.5 Storage

PLEASE CHECK ITS VALIDITY BEFORE USE

AN ELECTRONIC DOCUMENT.

A PRINTED COPY OF

5 H

THIS

All IPs should be kept in a secure place under appropriate storage conditions. A description of the appropriate storage and shipment conditions are specified on the IP label and in the IB.

# 5.6 Concomitant and post-study treatment(s)

The following concomitant medications and treatments are not allowed **prior** to enrolment:

• Chemotherapy or radiation therapies within 2 weeks prior to enrolment.

The following concomitant medications and treatments are not allowed after enrolment and

during the study:

- As they interfere with the disease under study:
  - PPIs or H2RAs (other than IP), sucralfate, and prostaglandins
  - Somatostatin and tranexamic acid or drugs with similar effect
  - Heparin
  - NSAIDs, COX- 2 inhibitors and ASA (including low dose) during the first 7 days of the study
  - Treatment of *H. pylori* infection. In case *H. pylori* infection has been detected, normal hospital routines should be adhered to, after the final visit, as judged by the investigator
- As there is a potential risk for drug-drug interactions with esomeprazole or cimetidine:
  - Warfarin (including other vitamin K antagonists), cisapride, phenytoin, atazanavir, nelfinavir, digoxin, methotrexate, clopidogrel, tacrolimus, teophyllin, lidocaine, nifedepine
- Due to patient vulnerability:

- Chemotherapy or radiation therapy
- To avoid non-significant bleeding being classified as rebleeding:
  - "Second look" endoscopy without clinical signs of rebleeding as defined in Section 6.3.1.1

Other medication, which is considered necessary for the patient's safety and well-being, may be given at the discretion of the investigator(s). The administration of all medication (including IPs) must be recorded in the appropriate sections of the eCRF. Endoscopy-related anaesthetic and sedative medication given according to normal routines should not be recorded in the eCRF.

If the patient reaches the events significant rebleeding, endoscopic re-treatment and/or surgery due to rebleeding, treatment will be stopped and the patient will be treated according to local guidelines. Restrictions for concomitant medications and treatments are not applicable in such cases. When the clinical situation permits, oral treatment with esomeprazole 40 mg tablets should be initiated/re-started.

# 5.7 Treatment compliance

PRINTED COPY OF AN ELECTRONIC DOCUMENT. PLEASE CHECK ITS VALIDITY BEFORE USE

IS A

THIS

The administration of all IPs should be recorded in the appropriate sections of the eCRF.

The i.v. treatment will be administered under the supervision of the study site personnel. The actual times of start and stop (and, if applicable, any stop and restart in between) as well as the infused volume and the infusion rate of the i.v. infusion, will be recorded in the eCRF.

During the open label oral treatment with esomeprazole 40 mg tablets, the patients will record intake of IP in the patient diary on a daily basis, and the investigator or delegate will check adherence to prescribed treatment at study visits.

Each patient is required to comply with the prescribed treatment regimen throughout the study and should be counselled on the importance of taking their IP as prescribed. The patients will be instructed to return all unused tablets at the follow-up visit/final visit. The tablet counts will be recorded in the eCRF.

# 5.7.1 Accountability

The IPs provided for this study will be used only as directed in the protocol.

It is the PI's responsibility to ensure that a procedure is established and maintained for the operation of the blinded and the unblinded IPs. This includes but is not limited to:

• The IPs are administrated only by the site staff named in the delegation of responsibility log.

- The unblinded nurse will account for the IP accountability including the IP acknowledge receipt at the site, the infusion bag preparation, the i.v. IP reconciliation and the drug destruction. Any discrepancies should be documented, investigated, and appropriately resolved
- The blinded nurse/site staff will be responsible for oral IP reconciliation.
- The blinded nurse will account for all IPs dispensed to and returned from the patient. The unused oral IP will be returned back to unblinded nurse after the reconciliation by blinded monitor.
- After i.v. administration, the used infusion bags will be returned back to the unblinded nurse and discarded according to hospital routines as soon as possible or at latest at the end of the day.

All used and un-used IPs will be sent back to local vendor for destruction according to local procedure. Destruction must not take place unless the responsible person at AstraZeneca has approved it.

The unblinded monitors will ensure the drug accountability record at clinical sites is maintained accurately.

# 5.8 Discontinuation of investigational product

Patients may be discontinued from study treatment at any time. Reasons for discontinuing a patient from IP may be:

- Patient decision. The patient is at any time free to discontinue treatment, without prejudice to further treatment
- Safety reasons as judged by the investigator and/or AstraZeneca (eg, histologically confirmed malignancy if routine biopsies were taken at visit 1)
- Adverse event, including event of rebleeding
- Eligibility criteria not fulfilled (see Section 5.3)
- Severe non-compliance to protocol as judged by the investigator and/or AstraZeneca
- Other reason specified by the investigator or AstraZeneca

If the patient is discontinued from IP, the scheduled study visits, data collection and procedures should continue according to the CSP until the follow-up visit. Alternatively, if the patient does not agree to this option, a modified follow up through e.g. telephone contact at the time-point of the follow-up visit should be arranged, if agreed to by the patient and in compliance with local data privacy laws/practices.

# 38(65)

# 5.8.1 Procedures for discontinuation of a patient from investigational product Discontinuation of treatment

If the study treatment is stopped, an unscheduled visit in the eCRF should be completed. After this visit, the patient should come for the follow-up visit on day 30(+5) and the assessments specified for the follow-up visit (Visit 3) should be completed and recorded in the eCRF. In addition to this, information regarding the event rebleeding, surgery and blood transfusion must be entered in the eCRF.

# 5.9 Withdrawal from study

Patients are at any time free to withdraw from study (IP and assessments), without prejudice to further treatment (withdrawal of consent). Such patients will always be asked about the reason(s) and the presence of any AE. If possible, they will be seen and assessed by an investigator and the assessments specified for the final visit should be completed and recorded in the eCRF. Patient diary and all IPs should be returned by the patient. AEs will be followed up by the investigator for as long as medically indicated, but without further recording in the eCRF (see Sections 6.4.3 and 6.4.4).

Reasons for withdrawal from the study may include, but are not limited to

- Patient decision. The patient is at any time free to discontinue their participation in the study, without prejudice to further treatment.
- Eligibility criteria not fulfilled
- Death
- AE
- Severe non-compliance with protocol, defined as refusal or inability to adhere to the CSP requirement
- Patient lost to follow-up
- Other, with specification given.

Withdrawn patients will not be replaced. For all patients who have received IP but have discontinued from the study, the investigator should make every possible effort to check that the patient is not reported dead within 30 days after randomisation.

Date

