#### Haematology:

PLEASE CHECK ITS VALIDITY BEFORE USE

ELECTRONIC DOCUMENT.

AN

A PRINTED COPY OF

5 H

THIS

- Hb
- B-White blood cell count (WBC)
- B-Platelets

In addition, a serology test for *H. pylori* will also be performed before the i.v. treatment.

Samples for clinical laboratory tests will be obtained by standardised techniques and assessed by a central laboratory for haematology and serum chemistry and *H. pylori* infection. Sample collection, labelling, storage and shipment will be described in a laboratory manual, which will be distributed by the central laboratory before the first patient is randomised. The samples may be taken in a patient whether he/she is fasting or not since the intra individual changes are the ones studied. The procedures used for individual patients should be kept constant.

The central and local laboratories will provide the investigator and AstraZeneca with test results including units, relevant reference ranges and updates as necessary. The result of local lab testing should be entered in the relevant eCRF.

The investigator must assess all laboratory results. If the measurements before i.v. treatment reveal any clinically relevant abnormal finding, incompatible with study participation as judged by the investigator, the patient should be discontinued from the study.

Calculated risk to individuals and community of the biological sample handling are expected to be none or very low as defined by the World Health Organisation (WHO). No blood samples will be taken from patient of high infective risk, as judged by the investigator.

**NB**. In case a patient shows an AST or ALT  $\geq$ 3xULN or total bilirubin  $\geq$  2x ULN please refer to Appendix E. Actions required in cases of combined increase of Aminotransferase and Total Bilirubin – Hy's Law', for further instructions. Laboratory testing of such cases (Hy's law

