## 13.3.1 Maternal exposure

Pregnant women, as well as those who are planning pregnancy or are breast-feeding, are excluded from the study. In addition, fertile women not using acceptable contraceptive measures, as judged by the investigator, should not be included in the study. Clinical experience with esomeprazole in pregnant women is limited and patients that become pregnant must be discontinued from the study.

If a patient becomes pregnant during the course of the study, IP should be discontinued immediately.

Pregnancy itself is not regarded as an AE unless there is a suspicion that the IP under study may have interfered with the effectiveness of a contraceptive medication. Congenital abnormalities/birth defects and spontaneous miscarriages should be reported and handled as SAEs. Elective abortions without complications should not be handled as AEs. The outcome of all pregnancies (spontaneous miscarriage, elective termination, ectopic pregnancy, normal birth or congenital abnormality) should be followed up and documented even if the patient was discontinued from the study.

If any pregnancy occurs in the course of the study, then investigators or other site personnel inform appropriate AstraZeneca representatives immediately, or **no later than 24 hours** of when he or she becomes aware of it.

The designated AstraZeneca representative works with the investigator to ensure that all relevant information is provided to the AstraZeneca Patient Safety data entry site within 1 or 5 days for SAEs, see Section 6.4.4 and within 30 days for all other pregnancies.

The same timelines apply when outcome information is available.

The PREGREP module in the eCRF is used to report the pregnancy and the PREGOUT is used to report the outcome of the pregnancy.

61(65)

A PRINTED COPY OF AN ELECTRONIC DOCUMENT. PLEASE CHECK ITS VALIDITY BEFORE USE

5 H

THIS

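### Section 5.9 allows a consenting patient to be withdrawn from assessments for reasons that Section 5.8 handles with continued follow-up, and the missing outcome then counts as no rebleeding

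*Protocol*

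**What the plan says.** **Stopping product (5.8, 5.8.1).** Section 5.8 lists among its reasons "Adverse event, including event of rebleeding", unmet eligibility with a pointer to Section 5.3, and "Severe non-compliance to protocol as judged by the investigator and/or AstraZeneca". The consequence is explicit: "If the patient is discontinued from IP, the scheduled study visits, data collection and procedures should continue according to the CSP until the follow-up visit". Telephone contact is the fallback for a patient who does not agree to visits. Section 5.8.1 also requires rebleeding, surgery and transfusion data to be entered.

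**Leaving the study (5.9).** Withdrawal covers product and assessments and is introduced as withdrawal of consent. The list that follows, "Reasons for withdrawal from the study may include, but are not limited to", goes beyond consent: it names unmet eligibility, death, AE, severe non-compliance (here defined as refusing or being unable to follow the protocol) and loss to follow-up. A final-visit assessment is done if possible. AEs are then followed medically but no longer entered in the eCRF. For dosed patients who leave, the investigator checks for death within 30 days of randomisation. Withdrawn patients are not replaced.

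**Two sections that direct study discontinuation.** Under 6.4.5, if a pre-infusion measurement is "incompatible with study participation as judged by the investigator, the patient should be discontinued from the study". The same section refers to 5.9 for premature discontinuation from the study. Under 13.3.1, "patients that become pregnant must be discontinued from the study", while another sentence there speaks only of stopping product.

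**Analysis (12.1.1, 12.2).** The full analysis set (FAS) is every randomised patient who started the bolus. A patient who leaves early without a rebleed is counted as not having rebled.

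**The concern.** For an AE or non-compliance, two sections give different answers to the question of whether data collection continues, and nothing says which governs when the patient still consents. One site may follow 5.8 and keep the patient to day 30. Another may follow 5.9 and close the record. The second choice produces a missing outcome that 12.2 turns into a favourable one. Because the synopsis makes the aim a descriptive comparison with the global study, a one-directional error bears on the main reading of the trial.

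Safety is affected too. Sections 3.2 and 12.3 base 100 patients per group on safety data, and a patient withdrawn for an AE is one whose later AE record matters most. A statistical analysis plan cannot recover outcomes that were never collected, so this has to be settled in the protocol.

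**Working it through.** **Step 1. Which route applies?**

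| Situation | Follow-up kept by | Follow-up ended by | Settled? |
|---|---|---|---|
| AE | 5.8, 5.8.1 | 5.9 (permits) | No |
| Severe non-compliance | 5.8 (judged by investigator or sponsor) | 5.9 (permits; refusal or inability) | No |
| Ineligible, not yet randomised or treated | – | 5.3 | Yes; outside the FAS if no bolus |
| Ineligible, dosed, product stopped | 5.3 sends to 5.8.1 | 5.9 repeats the reason without this limit | By 5.3, but 5.9 is not aligned |
| Abnormal pre-infusion finding | – | 6.4.5 (directs) | Ends study; in the FAS only if the bolus had begun |
| Pregnancy | – | 13.3.1 (directs) | Ends study, although another sentence there stops product only |

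**Step 2. What is collected after a 5.9 withdrawal?** One assessment if possible, then vital status. Rebleeding, re-treatment, surgery and transfusion after that point are not sought.

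**Step 3. Size.** The protocol states no withdrawal rate and no figure on this point, so there is nothing to reproduce. Let *p* be the rebleeding rate, *w* the share of an arm that leaves before any event, and *m* the risk in leavers relative to *p*.

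- Reported rate = (1 − *w*)·*p*
- True rate = (1 − *w*)·*p* + *w*·*m*·*p*
- Understatement = *w*·*m*·*p*

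Inputs for *p*: 5.9% at 72 hours on esomeprazole in the global study, and 10–20% in the first month (both Section 1.1). Assumed: *w* = 5%, 10%, 15%, and *m* = 1.

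| *p* | *w* = 5% | *w* = 10% | *w* = 15% |
|---|---|---|---|
| 5.9% (72 h) | 0.05 × 5.9 = 0.30 | 0.59 | 0.88 |
| 10% (30 d) | 0.50 | 1.00 | 1.50 |
| 20% (30 d) | 1.00 | 2.00 | 3.00 |

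Entries are percentage points. With *m* = 2 each entry doubles; with *m* = 0.5 it halves. For example, at *p* = 5.9% and *w* = 10%, the reported rate is 0.90 × 5.9 = 5.3%.

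Only patients who leave within 72 hours count towards the first row, while anyone leaving by day 30 counts towards the others. The share *w* is therefore no larger at 72 hours than at 30 days, and the main effect falls on the 30-day outcomes.

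**Step 4. Safety.** With 100 per arm, the same assumed 5–15% means 5 to 15 patients per arm with AE recording cut short.

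**The case against.** The strongest reply is that 5.9 orders nothing. It starts from the patient's own decision, its list says what reasons may be, and it includes death and loss to follow-up, so it can be read as a set of disposition codes. The eCRF field in 6.4.3 on whether an AE caused study withdrawal fits that reading. On this view 5.8 is the working rule. This stands in part: 5.9 permits an end to assessments and does not require one. But it does not say that 5.8 prevails, and 6.4.5 and 13.3.1 are directive.

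Other points that stand:

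- Ineligibility is largely settled by 5.3. What remains is that 5.9 does not carry the limit over.
- Some non-compliance under 5.9 is refusal, where outcomes could not be collected under any wording.
- A reader might infer that the pre-infusion central laboratory results usually arrive after the infusion has begun, so that these patients are generally in the FAS. The protocol gives no turnaround time. A patient removed before the bolus is not in the FAS.
- Safety follow-up is reduced, not absent. Section 3.1 provides an unscheduled visit at discontinuation, 6.4.5 a laboratory screen, and 6.4.3 lets the sponsor ask for more on ongoing events.
- Within 72 hours, patients are supervised and checked every 8 hours, and those who rebleed are told to continue the study (3.1, 5.5.2), so loss is least likely there.

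A reader might also set 3 to 5 unknown outcomes per 100 against roughly 6 expected events and call the problem 50–83% of the events. That compares patients with events, and it would be the effect only if nearly every leaver rebled. At 5% loss and equal risk, the expected loss is 5 × 0.059 ≈ 0.3 events. A 1-point understatement at that loss would need 1 ÷ 0.295 ≈ 3.4 times the average risk, and the protocol gives no figure to support that.

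**Conclusion.** The inconsistency is real and worth correcting, but its expected effect is modest. For a consenting patient with an AE or non-compliance, the protocol permits two incompatible data-collection routes. For abnormal pre-infusion findings and pregnancy it directs study discontinuation. Where such a patient has started the bolus and has no recorded rebleed, the scoring rule can only lower the reported rate.

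Under an assumed 5–15% withdrawal and equal risk, the understatement is about 0.3–0.9 points at 72 hours and 0.5–3.0 points at 30 days, twice that if leavers carry twice the risk. The withdrawal rate and the relative risk are both assumptions. That leavers are sicker is plausible but not shown. The analysis is descriptive, so an estimate is affected and no test is. The larger consequences are for the 30-day outcomes and the safety record.

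**What to change.** - **5.9:** limit withdrawal from assessments to withdrawal of consent, loss to follow-up and death. State that AE, non-compliance and ineligibility found after dosing are handled under 5.8, and carry over the 5.3 limit.
- **6.4.5 and 13.3.1:** reconcile these with 5.8 for patients who have been dosed, so that discontinuation does not by itself end data collection.
- **Data to continue to day 30 where the patient consents:** rebleeding, endoscopic re-treatment, surgery, transfusion and AEs, with the telephone fallback that 5.8 already provides.

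The change concerns data collection only; decisions on treatment stay as they are. It is a short amendment to three sections, and the running cost is a few extra follow-up contacts.
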